## 6.2 Non-inclusion criteria

Patients will not be eligible for study enrollment if they have one or more of the following criteria:

1. Any treatment (including medications, medical devices and food supplements) that can influence the stool consistency, according to the Investigator's opinion should not be used within 14 days prior to Visit 1;
2. Use of anti-rejection medication after stem cell or solid organ transplant;
3. Use of glucocorticosteroids within the last 8 weeks prior to the study start;
4. Use of proton pump inhibitors within 3 months prior to Visit 1;
5. Chemotherapy or radiation;
6. History of recurrent diarrhea;
7. Patient has diarrhea or loose stool in the last 2 days prior to the study start;
8. Patient has severe ARD expected to require an administration of additional antibiotics or antibiotics therapy for more than 7 days;
9. Use of antimicrobials in the last 3 months prior to the study start;
10. Use of yeast/probiotic/fermented products within the last 2 weeks prior to the first visit;
11. Known allergy/sensitivity to the investigational medicinal product;
12. Immunocompromised patients;
13. Patients with digestive / absorption disorders of the gastrointestinal tract (for example, inflammatory bowel disease, celiac disease, pancreatitis, motility disorders, etc.) and / or patients who underwent surgery on the organs of the gastrointestinal tract (with the exception of appendectomy more than 3 months prior to Visit 1);
14. Known irritable bowel syndrome;
15. Known small intestinal bacterial overgrowth;
16. Patients with pyrexia over 38°C;

17. Pregnant and/or breastfeeding women;
18. Participation in other clinical trials of medicinal products or medical devices at the screening Visit or for 30 days before the screening Visit;
19. Surgical intervention within 30 days before the screening visit or planned surgical treatment during the trial (before a follow-up visit is completed), including diagnostic procedures or inpatient stay;
20. Known or suspected alcohol and/or drug addiction;
21. A suspected low compliance or incapability of the patient to perform the procedures and comply with restrictions according to the trial protocol (e.g., due to mental disorders);
22. Potential for translocation of probiotic across bowel wall (active bowel leak, acute abdomen, active intestinal disease including colitis, or significant bowel dysfunction; presence of neutropenia or anticipation of neutropenia after chemotherapy; radiation therapy);
23. Any diseases of cardiovascular, renal, hepatic, gastrointestinal, endocrine and nervous systems, or other conditions/diseases which, in the Investigator's opinion, may render study participation unsafe for a patient or may affect a test result;
24. A positive result of a rapid test for the detection of immunoglobulin M (IgM) antibodies to COVID-19.

### **6.3 Exclusion Criteria**

#### **6.3.1 Timing and terms of subject exclusion from the study**

Subjects can be excluded from the study of their own free will at any time without explanation, as well as by decision of the physician investigator or Sponsor, in cases where continued participation in the study poses a threat to the health and/or life of the patient. In addition, the patient will not be able to continue participating in the study for the following reasons:

Subject participation will be stopped in case any of the following reasons occur:

1. Disease progression (including pyrexia above 38°C for 3 days or longer);
2. Positive results of culture or PCR for the dysentery group, typhoid fever group, pathogenic E. coli and other pathogenic groups (incl. Cl. difficile), the treatment of which requires the prescription of additional antibiotic therapy;
3. Need to change tactics of antibacterial therapy (extension course of antibacterial therapy or change of antibiotic group);

4. The Ethics Committee, regulatory authorities, or Sponsor can terminate the clinical study or participation of the specific trial site in the study for any reason;
5. The investigator decided that the patient must be withdrawn from the study for the own interests of the patient;
6. Informed consent withdrawal (patient reluctance to continue to participate in the study);
7. Individual intolerability of Investigational medicinal products according to Investigator's judgment;
8. Occurrence of clinically significant adverse event or serious adverse event in the patient;
9. Patient's non-compliance;
10. Error enrollment (e.g., the patient was included with violation of the inclusion/non-inclusion criteria);
11. The patient complies with the non-inclusion criteria during the study;
12. The patient receives/requires an additional treatment which might influence the study results or patient's safety (see "Prohibited concomitant therapy" section);
13. Other conditions or events which, in the Investigator's judgement, require the patient's exclusion from the study.

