|                                  | 
intestinal disease including colitis, or significant bowel dysfunction; presence of neutropenia or anticipation of neutropenia after chemotherapy; radiation therapy);
 
23. Any disorders of cardiovascular, renal, hepatic, gastrointestinal, endocrine, or nervous disorders, and other conditions/diseases which, in the Investigator's opinion, may render study participation unsafe for a patient or may affect a test result.
 
24. Positive result of express-test for detection of IgM antibodies for COVID-19.
   |
| 
Exclusion Criteria
 | 
Subject participation will be stopped in case any of the following reasons occur:
 
 
1. Disease progression (including pyrexia above 38 °C for 3 days or longer);
 
2. Positive culture or PCR results for Shigella and Salmonella spp, typhoid and paratyphoid species, pathogenic E. coli, and other pathogen species (including C. difficile), if supplementary antibacterial treatment is required during the study;
 
3. Need to change tactics of antibiotic therapy (extension course of antibiotic therapy or change of antibiotic group);
 
4. The Ethics Committee, regulatory authorities, or Sponsor terminate the trial or participation of the specific trial site for any reason;
 
5. The Investigator's decision to withdraw the patient from the trial in the interests of the patient;
 
6. Withdrawal of the informed consent (unwillingness of the patient to continue his/her participation in the study);
 
7. Individual intolerance of Investigational products (according to Investigator's judgment);
 
8. Clinically significant adverse event or serious adverse event;
 
9. Patient's non-compliance;
 
10. Error enrollment (e.g., the patient was included with violation of the inclusion/non-inclusion criteria);
 
11. The patient complies with the non-inclusion criteria during the study;
 
 |

|   |  |
|---|--|
|   | 
12. The patient receives or requires an additional therapy which might influence the study results or patient's safety (see Prohibited concomitant therapy section);
 
13. Other conditions or events which, in the Investigator's opinion, require the patient's exclusion from the study.
  |

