## 5. Study Design

### 5.1 Main and additional studied parameters

#### 5.1.1 Efficacy parameters

##### 5.1.1.1 Primary efficacy parameter

An assessment of frequency of occurrence of AAD from 1 to the last day of LRG-002 administration compared with placebo in antibiotic-treated patients with ARDs, receiving standard antimicrobial therapy is selected as the primary efficacy endpoint. The primary efficacy criterion will be considered achieved if the odds ratio for the AAD incidence between two groups is significantly higher than 1 (i.e. AAD incidence in the LRG-002 group is lower than in placebo group).

*AAD is defined as diarrhea associated with the AB use caused by C. difficile or of otherwise not identified etiology, upon analysis of stool samples and differential diagnostics according to investigator's judgment.*

*Diarrhea is defined as loose or watery stool (Type 5-7 according to Bristol Stool Form Scale) three times a day (frequent bowel movements with formed stool is not considered as diarrhea) in accordance with WHO criteria; based on the diary data (BSFS) and confirmation of AAD by the investigator.*

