#### 5.2.3.2.5. *Collection of stool samples*

Stool samples are collected in case of diarrhea by patients of both groups. Samples will be collected in containers dispensed in advance with the appropriate labeling:

- 1 container - a stool sample for presence of common diarrheal pathogens - Rotavirus, Adenovirus, Norovirus, Campylobacter spp, Salmonella spp, Shigella spp.;
- 1 container – stool sample for presence of *C. difficile* toxins A and B;
- 1 container - collection of stool samples for the culture of opportunistic flora: *Klebsiella pneumoniae*, *Staphylococcus aureus*, *Proteus mirabilis*, *Candida* spp, *E. Coli*, and culture of *Yersinia* spp. (special container). A detailed description of the procedure of stool sample collection and instructions for the patients are provided in Appendix 2.

The drugs for the treatment of acute diarrhea can be used only in case of acute diarrhea, namely: the presence of liquid, watery stools (Type 6, 7 on the Bristol scale) with a frequency of 3 or more times within 24 hours).

Patients will be instructed that in the case of acute diarrhea (the presence of liquid, watery stools (Type 6, 7 on the Bristol scale) with a frequency of 3 or more times within 24 hours), the physician

investigator will prescribe an oral rehydration therapy to the patient, as well as give diet recommendations.

After the third stool of type 6 and/or 7, the patient should consult the physician investigator and get medical advice before using any remedy for acute diarrhea.

If the patient has stools of type 6 and/or 7 according to the Bristol scale at least three times a day, the physician investigator will prescribe an oral rehydration therapy to the patient, give recommendations on the diet and can instruct the patient about the possibility of using additional drugs to relieve symptoms of acute diarrhea.

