#### ***6.3.1.1 Timing and volume of data collection for excluded subjects.***

If the subject is excluded from the study at his/her request, the investigator should try to find out the reason for the termination of the study. If the study is terminated due to the occurrence of AE/SAE, monitoring of the subject continues until AE/SAE resolution. In case of premature termination of the patient's participation in the study, the patient is invited to the study site to carry out the procedures of premature study termination visit (carried out within the frameworks of unscheduled visit); if the patient refuses to visit the study site, the premature study termination visit is carried out by phone, while as much as possible the available information is recorded.

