### **7.3 Allowed concomitant treatments**

Oral beta-lactam antibiotic (eg, amoxicillin, amoxicillin + clavulanic acid, cefixime, etc.) (See Background antibacterial therapy) according to inclusion criterion 3, at the same dosage as at the study initiation.

Continuation of the drug administration, started prior to the inclusion into the study for treatment of concomitant diseases and not covered by any exclusion criterion. Female participants taking oral contraceptives may continue to take them during the study.

Standard symptomatic treatment agents used to treat acute respiratory infections (in case of medical need), including anilides, triazole derivatives, with the exception of drugs that can induce a laxative effect (for example, throat lozenges with sugar substitutes).

Agents for relieving symptoms of acute diarrhea (in case of medical need), including electrolyte solutions, with the exception of sorbents.

Prescribing therapy for acute diarrhea and symptomatic therapy for ARDs is possible only by the decision of the Investigator.

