### **9.3 Requirements for reports, procedures on recording and reporting of adverse events and intercurrent diseases**

#### **9.3.1 Terminology of adverse events and serious adverse events**

**Adverse event (AE)** — any medically unfavorable event identified in a patient or subject in a clinical trial after the use of medicinal product, which may not have a causal relationship with its use.

Thus, an adverse event (AE) may be any adverse and undesirable clinical sign (including laboratory deviation from the norm), symptom or disease, the time of occurrence of which does not exclude a causal relationship with the use of the drug, regardless of the presence or absence of such a relationship.

**Serious adverse event (SAE)** — any adverse medical event that regardless of the dose of the medicinal product:

- causes fatal outcome;
- is life threatening;
- requires hospitalization or its extension;
- results in persistent or significant disability/incapacity;
- is a congenital anomaly or malformation;
- is clinically relevant: the decision about whether the express reporting is appropriate in other situations (e.g., in cases of medically important events that do not pose an immediate threat to the patient's life, do not result in death or hospitalization, but put the patient at risk or require intervention to prevent one of the above outcomes given in the definition) is made on the basis of a medical and scientific assessment. Such cases should also be considered as serious adverse events.

These characteristics / consequences must be considered at the time of event occurrence. For example, the concept of life-threatening AE refers to a medical event in which a subject is at risk of death at the time of the AE development; it does not refer to a medical event that could hypothetically cause death in case of a higher severity condition.

**(Serious) adverse reaction ((S)AR)** — any (S)AE for which there is a reasonable probability of a causal relationship with the use of the medicinal product in the opinion of the Investigator or Sponsor (see paragraph 8.8.3 below).

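### When severe AAD ends participation, no text keeps the stool diary going or has it collected, so diary-based secondary endpoints can be cut short in the worst cases

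*Protocol*

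**What the plan says.** **Stop rules.** Protocol 6.3.1 ends participation under item 8 for "Occurrence of clinically significant adverse event or serious adverse event in the patient"; the synopsis exclusion criteria carry the same item as "Clinically significant adverse event or serious adverse event". Item 2 does so for positive culture or PCR results in listed pathogens and "other pathogenic groups (incl. Cl. difficile), the treatment of which requires the prescription of additional antibiotic therapy".

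**Outcome.** Protocol 5.1.1.1 states: "AAD is defined as diarrhea associated with the AB use caused by C. difficile or of otherwise not identified etiology". C. difficile diarrhea is therefore a primary-endpoint event. Under 9.3.1 an event is serious if, among other criteria, it "requires hospitalization or its extension".

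**Ordinary AAD stays on study.** For acute diarrhea, 5.2.3.2.5 says "the physician investigator will prescribe an oral rehydration therapy to the patient, give recommendations on the diet", and 7.3 permits "Agents for relieving symptoms of acute diarrhea (in case of medical need), including electrolyte solutions, with the exception of sorbents".

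**After a stop.** Under 6.3.1.1, if the stop was for an AE or SAE, "monitoring of the subject continues until AE/SAE resolution". A termination visit is held in the format of an unscheduled visit, or by phone if the patient declines to attend. Under 6.3.2 study product ends with exclusion.

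**Visit content.** The compulsory list in 5.2.4.4, repeated in SAP 2.2.3, covers physical examination, vital signs, ECG, adverse events and concomitant treatment. Anything else is at the Principal Investigator's decision. Table 6 adds diary compliance and diarrhea classification at unscheduled visits, but marks collection of the diary at Visit 3 only.

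**Analysis.** SAP 3.2 limits any filling-in of missing values to the primary endpoint. SAP 7.2 compares durations, stool frequency and symptom severity by the Mann–Whitney–Wilcoxon test, gives no rule for an episode that has not ended, and declares all secondary analyses investigational.

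**The concern.** The AAD cases most likely to end participation are the severest: those hospitalised, those judged clinically significant, and C. difficile cases needing a further antibiotic. For these patients the instrument that measures the episode has no instruction to continue once participation ends.

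Duration of AAD and of any diarrhea, daily stool frequency, stool consistency and gastrointestinal symptom severity are all listed in Protocol 8.2 as diary endpoints. If the record ends at the stop, a long episode enters the analysis as a short one or drops out. Missingness then depends on the outcome being measured, and an available-data analysis does not correct for that. The direction of any bias between arms cannot be settled from the documents. If severe AAD is more common on placebo, truncation would fall mainly there and could hide a benefit of LRG-002.

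**Working it through.** **1. The plan's own figure.** Inputs from Protocol 10.3 and 10.4: AAD 0.26 on placebo and 0.15 on LRG-002, two-sided alpha 0.05, power 80%, allocation 1:1, attrition 20%.

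n = (1.960 + 0.842)² / (0.26 − 0.15)² × [0.26 × 0.74 + 0.15 × 0.85] = 7.849 / 0.0121 × 0.3199 = 207.5, rounded up to 208 per arm; 208 / 0.80 = 260 per arm.

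The stated 208 and 260 reproduce. Nothing in this point alters them.

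**2. How many AAD episodes feed the duration endpoint.** 260 × 0.26 = 67.6 on placebo and 260 × 0.15 = 39.0 on LRG-002, or 106.6 in all.

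**3. Which of these can be stopped.** Only AAD that is an SAE or a clinically significant AE (item 8), or C. difficile AAD needing added antibiotics (item 2). No section gives or implies the share. Each 1% of AAD cases stopped puts 106.6 × 0.01 = 1.07 duration records at risk (0.68 placebo, 0.39 LRG-002 if the share is equal by arm). Purely as assumptions, 5% would be 106.6 × 0.05 = 5.3 records and 10% would be 106.6 × 0.10 = 10.7.

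**4. What the endpoints need, against what the text requires after a stop.**

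| Needed | Required after a stop? |
|---|---|
| Diary up to the stop is reviewed | Yes in person: Table 6 marks diary compliance and diarrhea classification at unscheduled visits. Uncertain if the visit is by phone |
| Diary is collected | No: absent from 5.2.4.4; Table 6 marks Visit 3 only |
| BSFS and symptom entries continue to normalization | No text |
| AE course and outcome | Yes: 6.3.1.1 and 9.3.4 |

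**5. Can AE follow-up replace the diary?** The duration endpoint (5.1.1.2) runs from onset until stool form is back to BSFS types 1–4, with a 48-hour condition on normal stool. An investigator's AE resolution date records neither stool type nor the 48-hour condition. It also says nothing about daily frequency or symptom scores.

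**6. What the SAP then does.** With no filling-in (3.2) and no censoring rule (7.2), a truncated episode is either analysed at its truncated length or left out.

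**The case against.** The best defence is that the protocol is far from silent. A reader might infer that AAD in general ends participation; 5.2.3.2.5 and 7.3 show that it does not. A reader might infer that stopped patients are not followed. They are: 6.3.1.1 follows AE and SAE stops to resolution, and 9.3.4 requires AE treatment and outcome in the CRF. It also follows SAEs open at the last visit: until resolved or stable if related to product, otherwise for up to 30 days. C. difficile diarrhea meets the AE definition in 9.3.1, so item 2 stops are covered as well. Diary review at unscheduled visits is marked in Table 6. All of this stands.

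A further argument is that the empty Table 6 cell is a matter of layout, since return of unused product is also marked at Visit 3 only. That is fair as far as it goes: the cell forbids nothing. But product return is also dealt with in 5.3.3 and 5.3.5. No other section supplies a duty to collect the diary at early termination, and none continues it.

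Sections 9.3.4 and 9.3.5 mention discontinuing product for an AE and a subject who stays in after an SAE. A reader might see a contradiction with 6.3.1. These are general action and status fields, compatible with a stop, and the point does not rest on them.

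Finally, stool form after an item 2 stop reflects the added antibiotic too. That is true, and it limits what those extra days can show.

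**Conclusion.** The gap is real and modest. As written, the plan can truncate diary-based secondary endpoints in the severest AAD cases, in a way that depends on outcome, and the SAP has no rule for it. The number of patients is unknown and probably small: they are outpatients aged 18 to 65, severe respiratory disease and bowel disorders are excluded, and ordinary AAD is managed on study. The only firm figure is the roughly 107 expected AAD cases, which itself rests on the planning rates and full enrolment.

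Two stronger conclusions are not supported. A reader might infer that the primary analysis loses events. It does not lose an AAD already recorded: each patient counts once (10.1.2), classification can follow the laboratory result, and the ITT set in 10.8 keeps the patient. A reader might also infer a loss of per-protocol power, because stopped patients fail the per-protocol definition. That exclusion follows from the stop itself, not from the diary gap. Its size would rest on an invented share, and continuing the diary would not reverse it.

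This is a cheap improvement worth making, not a threat to the main result.

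**What to change.** 1. In 6.3.1.1 and 6.3.2, state that a patient meeting item 2 or 8 because of AAD stops study product but, with consent, continues the existing diary (stool times, BSFS, symptoms, rescue use) to Visit 3. Day 15 + 2 = Day 17, which is within the stated maximum and within the Appendix 3 pages. Word the synopsis exclusion criteria to match.
2. Add diary review and collection to the termination visit in 5.2.4.4 and Table 6.
3. In SAP 7.2, treat episodes unresolved at the last diary entry as censored, and name a test that accepts censored durations, since the planned Wilcoxon function does not. Censoring at a stop caused by severity is itself informative, so this backs up item 1 and does not replace it.
4. List stopped AAD cases by arm, with the reason and the last diary day.

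Cost: a protocol amendment of a few sentences and a table mark, a short SAP addition, and a few extra diary days in a small number of patients. Clinical discretion to stop product and treat is unchanged. Stool data after an item 2 stop should be reported with the caveat that they also reflect the added antibiotic.

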#### **6.3.2 Terms and conditions of stopping/termination by the subject of treatment with the medicinal product under study**

Patients stop taking the study medicinal products upon completion of their participation in the study in accordance with the protocol or upon their exclusion from the study.

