#### **6.3.3 Replacing the discontinued patients**

Replacement of the patients who discontinued their study participation is not provided.

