#### 4. Body temperature

[figure not shown]
Measure the body temperature in the axillary cavity with a mercury thermometer and record the result: \_\_\_\_\_

Comments \_\_\_\_\_ and  
complaints: \_\_\_\_\_

[figure not shown]

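### Protocol 6.3.1 item 11, read with non-inclusion item 16, makes the 3-day fever condition in item 1 redundant, so sites may stop different patients for the same brief fever

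*Protocol*

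**What the plan says.** Protocol 6.3.1 introduces its list with "Subject participation will be stopped in case any of the following reasons occur". Three entries bear on fever:

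- 6.3.1 item 1: "Disease progression (including pyrexia above 38°C for 3 days or longer". Fever is given here as an example of disease progression, and it carries a duration.
- 6.3.1 item 11: "The patient complies with the non-inclusion criteria during the study". No criterion is excepted.
- 6.2 item 16, which item 11 brings in: "Patients with pyrexia over 38°C". It has no duration.

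The synopsis has the same structure. Its exclusion item 1 reads "Disease progression (including pyrexia above 38 °C for 3 days or longer", and its exclusion item 11 and non-inclusion item 16 match the body. No section ranks item 1 and item 11 or limits item 11 to some of the criteria.

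Every diary page in Protocol Appendix 3 asks for temperature: "Measure the body temperature in the axillary cavity with a mercury thermometer and record the result". Protocol 5.2.3.2.6 has the investigator assess it, and Table 6 schedules a check of the exclusion criteria at Visits 2 and 3 and at unscheduled visits.

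Under Protocol 6.3.2, study product ends on exclusion. Protocol 6.3.1.1 provides an early termination visit, or a phone call if the patient will not attend. It plans no collection of AAD data after that; only adverse events are followed to resolution. On replacement, 6.3.3 says: "Replacement of the patients who discontinued their study participation is not provided".

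**The concern.** Two entries in one stopping list treat the same clinical event differently. All participants have an active acute respiratory disease, so a fever shorter than 3 days during the study is plausible, and the diary will record it. A site working from item 11 has grounds to stop that patient. A site working from item 1 has grounds to keep the patient. Both would be following the protocol.

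Withdrawal, time on study product and per-protocol membership would then depend partly on the site's reading. The primary endpoint runs from the first to the last day of LRG-002 administration, so a patient stopped early also has a shorter window in which AAD can be seen. The plan does not say whether a patient stopped without AAD counts as a non-event or as missing.

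**Working it through.** **Step 1: compare the two rules.**

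| On-study event | Item 1, fever clause | Item 11 with 6.2 item 16 |
|---|---|---|
| Fever above 38 °C, shorter than 3 days | not met | met as written |
| Fever above 38 °C, 3 days or longer | met | met as written |

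No fever meets the clause in item 1 without also meeting item 11. The 3-day condition therefore changes no decision if item 11 is applied as worded.

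**Step 2: is item 16 limited to screening?** Items 1, 3, 4, 7, 9, 10 and 18 of Protocol 6.2 are each tied to Visit 1, the study start or screening. Item 16 is not. The lead-in to 6.2 speaks of eligibility for enrolment, but item 11 carries the criteria into the study period without exception. A screening-only reading is possible; the text does not state it.

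**Step 3: what a stopped patient loses.**

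- ITT (Protocol 10.8; SAP 4.2.2) needs one dose and the Visit 1 procedures, so the patient stays in. AAD before exclusion counts.
- Per protocol (Protocol 10.8; SAP 4.2.3) needs the prescribed treatment and follow-up to be completed, so the patient drops out. The Study Population entry in the synopsis defines the 208 per arm as per-protocol patients.
- AAD between exclusion and the end of the planned 14 days is not observed. Protocol 10.6 and SAP 3.2 name a maximum-likelihood method for missing primary data, to be used if needed.

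**Step 4: reproduce the planned size.** Inputs from Protocol 10.3, 10.4 and SAP 2.3: rates 0.26 and 0.15, two-sided alpha 0.05, power 80%, ratio 1:1, attrition 20%.

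- Variance term: 0.15 × 0.85 + 0.26 × 0.74 = 0.1275 + 0.1924 = 0.3199
- n = ((1.960 + 0.842) / 0.11)² × 0.3199 = 207.5, rounded up to 208 per arm
- 208 / (1 − 0.20) = 260 per arm, 520 in total

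The plan's figures reproduce.

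**Step 5: illustration only.** Power from the same formula is Φ(0.11 / √(0.3199 / m) − 1.960), where m = 260 × (1 − loss) is the per-protocol number per arm. The documents give no rate of brief fever, so the loss values below are assumptions.

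| Per-protocol loss | m per arm | Power |
|---|---|---|
| 20% (plan) | 208 | 80.1% |
| 22% | 202.8 | 79.1% |
| 25% | 195 | 77.5% |
| 30% | 182 | 74.7% |

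**The case against.** The best reply is that this is an overlap and not a contradiction. The list is disjunctive, so items 1 and 11 can both hold. Item 1 is the only exclusion entry that names on-study fever, and a general clause is not usually read so as to empty a specific one. Item 16 also sits under an enrolment lead-in. This is a reasonable reading, and a reader who inferred that the two rules cannot both apply would go too far. What remains is that the text does not impose this reading on sites.

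A reader might also infer that one diary reading above 38 °C stops a patient at once. The procedures do not support that. Exclusion criteria are checked at visits, and the diary tells patients to call about loose stools but not about fever. A short early fever may have resolved by Day 7 ± 2. One first noticed at Visit 3 would normally cost no outcome time, because the 14-day course is then complete.

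A third inference would be that stopped patients vanish from the analysis or exhaust the 20% allowance. They remain in ITT, and an early termination contact and a method for missing primary data are both named. The 20% is a general withdrawal rate and may already cover some of these patients. Patients above 38 °C at entry are not enrolled, and symptomatic treatment of the respiratory disease is permitted; both may make on-study fever less common. These points stand and limit the size of the problem.

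**Conclusion.** The point holds as a conflict of wording within the stopping rules, present in both the body and the synopsis. Item 11 as written makes the duration in item 1 redundant, and sites may stop different patients for the same brief fever. The consequences are lost per-protocol membership and unobserved AAD for the rest of the planned period, with no replacement.

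The size is unknown. The power figures of 79.1%, 77.5% and 74.7% assume that total per-protocol loss rises to 22%, 25% or 30%; no document supports any of these values. They describe the per-protocol count and should not be read as a forecast or as a loss of ITT patients. Nothing in the documents shows a difference between arms. The case for acting rests on avoidable inconsistency across up to 40 sites and on how little the correction costs. This review takes no position on which fever rule is right.

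**What to change.** - Reconcile Protocol 6.3.1 items 1 and 11 with 6.2 item 16, and the matching synopsis entries, so that one on-study fever rule applies. The choice of rule belongs to the sponsor; none is proposed here.
- State that patients stopped under items 1 or 11 who do not withdraw consent are asked to continue the diary to the end of the planned 14-day period, and that their observed AAD status is used in the ITT analysis.

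The cost is a short clarifying amendment and some diary collection after study product has stopped. The patient already holds the diary from Visit 1, and its pages run to Day 17.
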